4 STUDY DESIGN**4.1 OVERALL DESIGN**

We will conduct a dialysis clinic-level cluster randomized trial with two groups, SPIRIT versus usual care followed by delayed SPIRIT. We will recruit 400 dyads of patients on chronic (“prevalent”) dialysis who are at high risk of death in the next year and their surrogate decision-makers (total 800 individuals) from 30 free-standing dialysis clinics in 4 states. The primary outcomes are patient and surrogate self-report preparedness for end-of-life decision making. The implementation evaluation data will be obtained throughout the study course. Upon patient death (anticipate 20% of patients; n = ~ 80), we will assess surrogates’ post-bereavement distress. Patient participation will end at 9 months (to allow for obtaining Medicare claims data during the study period) or death, whichever occurs first; surrogate participation will end at 9 months or at the completion of 3-month post-death follow-up. If patient is still living at 9 months, we will ask for an extension of follow up period to include 12 more months. Medicare claims data for end-of-life treatment intensity will be obtained quarterly. Clinics assigned to usual care will receive the delayed implementation, SPIRIT, in Year 4, Q1. This is a Phase III trial of an intervention that involves minimal risks and has proven to be efficacious, and thus no interim analysis is planned.

For Supplement Aims:

We will use a randomized controlled trial design with two groups: SPIRIT-dementia and usual care. From the pool of screened but excluded ESRD patients, we will recruit 30 dyads of patients with mild to moderate dementia and their surrogates. The groups will be stratified by race (white vs non-white). Patient and surrogate self-reported preparedness for end-of-life decision making will be measured at baseline and shortly after the intervention (by phone in the next 2-3 days) as done in the pilot test of SPIRIT-dementia. Additionally, we will review the patient's medical record to examine care decisions at 6 months or after the patient's death, whichever occurs first. In the case of patient death, we will also assess surrogates' post-bereavement outcomes (anxiety and depression symptoms) at 1 month after the patient's death. Based on previous research,¹³ we anticipate about 50% of the supplement sample will die within 12 months of enrollment. All data collection from study participants will be telephone-based.

Supplement cohort study:

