At the next monthly check in phone call (as part of the parent study protocol), the research staff member will proceed with the procedures for the parent study and then introduce the participant to the supplement study, including the purpose and procedures and obtain verbal consent. After both members of the dyad have consented, the recruiter will schedule two data collection calls (T3 within 1 week and T4 at 6 months). If additional subjects are needed, we will contact those who already completed the study before the pandemic.

To Maximize Participant Retention, we will

- a) obtain two backup contacts from each member of the dyad in the event that we cannot reach them by telephone and mail
- b) make confirmation phone calls 2 days prior to the baseline and/or the SPIRIT session (intervention group)
- c) make scripted monthly check-in calls
- d) send holiday cards
- e) assign the same data collector whenever possible
- f) provide transportation support (\$20) for the SPIRIT session in person at the center (intervention group)
- g) compensate each member of the dyad with gift cards (\$20 at baseline; \$25 at post-intervention follow-up; and surrogates who complete post-bereavement assessment will receive \$30 at 1 month after the patient's death).

For supplement cohort study, each member of the dyad will receive an additional \$20 at the completion of T3 and \$30 at T4.

Recruitment of Care Providers for Implementation data collection, we will obtain a list of dialysis care providers from each dialysis center, who are willing to be contacted by the study staff for participating in implementation related data collection. This data collection is to obtain inputs from the care providers regarding SPIRIT implementation as part of routine dialysis care. Research study staff at the study site will contact care providers on the list using their preferred contact numbers or emails. Verbal Care Provider Informed Consent will be used in consenting process. Survey/Interviews will be scheduled to be conducted over the phone or in person at the convenience of the Care Provider. There will be no compensation for care provider's participation.

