6.3 MEASURES TO MINIMIZE BIAS: RANDOMIZATION AND BLINDING

Clinics covered by the same care provider who will deliver SPIRIT sessions will be combined to one cluster to avoid risk of contamination; this results in clusters (4 in GA, 3 in NC, 8 in NM, 5 in PA and 8 in VA). Because the numbers of available patients substantially vary across the clusters, to minimize group imbalance clusters will be stratified to three sizes: small (patient census ≤ 52), medium (53-105), and large (≥ 106). We will randomize clusters to either SPIRIT or usual care plus delayed SPIRIT, with randomly permuted blocks (sizes of 2 and 4) within cluster size stratum nested in each state, using a pseudo-random-number generator, by the Study Coordination Center.

Before the study starts, the Study Coordination Center will inform the group assignment for each cluster to the site PIs, with a unique ID consisting of abbreviations for state and cluster size stratum. While the heterogeneity in minority race/ethnicity across clusters improves the study's generalizability, stratification or pairing clusters by race/ethnicity is not feasible because some clinics uniquely serve one race with no comparable clinics within state. Group imbalances on race/ethnicity and other potential confounding factors will be examined and adjusted for in the analyses. The cluster randomized design prevents blinding patient-surrogate dyads and dialysis care providers to group allocation. However, research staff assessing effectiveness outcomes will be blind to group assignment.

For Supplement Aims:

[name] (biostatistician/Co-I) will generate a randomization scheme using stratified (by race), permuted block randomization with block size 5, using a random-number generator. Dyads will be randomized with equal allocation (1:1) to SPIRIT or usual care. Due to the nature of the intervention, blinding dyads to their group allocation is impossible, but the research staff assessing outcomes will be blind. Immediately after the completion of the baseline assessment by phone, the data collector will open a sealed envelope to identify group assignment and schedule an intervention session to take place ~ 2 weeks hence for SPIRIT as well as a follow-up data collection session in the next 2-3 days.

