8 STUDY ASSESSMENTS AND PROCEDURES

8.1 OUTCOME ASSESSMENTS

Collecting effectiveness outcome data will be centralized; research staff at the Study Coordinating Center will collect the data from patients and surrogates by phone. Telephone-based collection minimizes participants' travel burden. Centralized data collection maintains data collectors being blind to group assignment. The preparedness outcomes will be assessed at 2 weeks post-intervention, as in our R21 trial.¹⁸ We expect roughly 40% of study patients (~160) to die by the 9-month follow-up; deaths are readily identifiable through dialysis clinics and will trigger post-bereavement surveys with surrogates at 3 months and staggered CMS data collection. Post-bereavement assessment at 3 months is based on our efficacy data showing that distress symptoms sharply rose in both groups 2-weeks post-bereavement and then stabilized at 3 months.

Effectiveness Outcomes

Preparedness for end-of-life decision making (measured at baseline and 2 wks post-Session II):

- **Dyad congruence** will be assessed using the Goals-of-Care Tool,^{18,20} which includes two scenarios describing medical conditions commonly occurring in ESRD patients. In the first, the patient develops a severe complication and cannot speak for himself/herself; the medical team believed recovery unlikely and continuing life-sustaining treatment, including dialysis, would no longer be beneficial. In the second scenario, the patient develops advanced dementia. Each scenario has three response options: "The goals of care should focus on delaying my death, and thus I want to continue life-sustaining treatment", "The goals of care should focus on my comfort and peace, and thus I do not want life-sustaining treatment, including dialysis", and "I am not sure". Patients and surrogates complete this tool independently and their responses are then compared to determine dyad congruence -- either congruent in both scenarios or incongruent. If both members of the dyad endorse "I am not sure", they are considered incongruent.
- **Patient decisional conflict** will be measured using the 13-item Decisional Conflict Scale (DCS), a validated measure in the context of end-of-life decision making¹⁷; higher scores indicate greater difficulty in weighing benefits and burdens of life-sustaining treatments and decision making (range 1-5; Cronbach's $\alpha = 0.8 - .93^{17,18,20,72}$).

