10.1.8 QUALITY ASSURANCE AND QUALITY CONTROL

We will use centralized training of research staff for recruitment and data collection activities as appropriate. The PI and Project Director will train staff in all study procedures. All project staff will complete university sponsored research integrity training, including modules on the protection of human subjects, HIPAA, and Good Clinical Practice. All roles, responsibilities, and a protocol with scripted subject contacts will be clearly delineated in the study Standard Operating Procedures (SOPs). These SOPs will be accessible via REDCap.

Data collectors/recruiters will attend a competency based, one-day training session that the PI and Project Director will convene. Following a demonstration by the PI or Project Director on how to recruit participants and obtain informed consent, the recruiters will be expected to perform three satisfactory practice recruitment sessions before actual performance. The final practice sessions will be audio- or video-recorded and reviewed for adherence to the protocol. After demonstrating satisfactory performance of consenting sessions, the recruiters will be authorized to recruit and enroll participants.

Training for data collection will include scripted data collection techniques with special attention to assessing participant fatigue or discomfort during the data collection session. Data collectors will conduct a series of three practice baseline and follow-up data collections using volunteers. After demonstrating satisfactory performance on data collection, they will be authorized to perform data collection activities with enrolled participants. They will also need to demonstrate completeness of data collection activities using REDCap.

Each study site will perform internal quality management of study conduct, data collection, documentation and completion. In general the following strategies will be employed:

- Use of data collection and data entry SOP
- Before ending the data collection session, review the data entry form in REDCap for any missing data
- Each data collector signs his/her work
- Audit research staff members' performance (e.g., consenting and data collection) Biannually.

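### Dementia pilot: the data collector opens the allocation envelope and stays with the dyad where possible, so the procedure does not secure the assessor blinding that Section 6.3 states

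*Combined protocol and SAP*

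**What the plan says.** Section 6.3, under Supplement Aims, accepts that dyads cannot be blinded and then offers one safeguard: "but the research staff assessing outcomes will be blind". The next sentence sets out allocation. Its timing is given as "Immediately after the completion of the baseline assessment by phone". As to who acts at that point, the plan says that "the data collector will open a sealed envelope to identify group assignment and schedule an intervention session". The same person also books the follow-up data collection.

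Section 5.5 lists among its retention measures: "assign the same data collector whenever possible". Section 4.1 says of the pilot: "All data collection from study participants will be telephone-based". Section 10.1.8 describes training for the role: "Data collectors will conduct a series of three practice baseline and follow-up data collections using volunteers".

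Section 6.2.1, describing the pilot's SPIRIT session, gives the booking of the follow-up call to the interventionist instead. Section 8.1 has the research coordinator track the pilot's care decisions through the dialysis nurse practitioner.

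**The concern.** Masking the assessor is the only blinding the pilot claims. The person who opens the envelope learns the arm before any post-baseline outcome has been collected. If that person then makes the outcome call, the safeguard has failed for that dyad, and the plan's own continuity rule makes that the expected arrangement.

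The outcomes at stake are goals-of-care congruence, patient decisional conflict and surrogate confidence at 2-3 days, and the surrogate's anxiety and depression scores at 1 month after a death. All are collected in conversation with cognitively impaired patients or their surrogates. An interviewer who knows the arm can prompt, repeat or clarify differently between arms without intending to. Section 9.2 says that the pilot's effect sizes will feed the sample size calculations of later studies, so a bias here would carry forward. A report that called the assessors masked could also be inaccurate.

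**Working it through.** No formula applies and no figure in the plan needs reproducing. The check is whether the blinding statement survives the procedures around it.

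1. **When the arm becomes known.** Section 6.3 places the opening of the envelope after the baseline assessment. Baseline scores are therefore protected, but every later assessment is open to influence.

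2. **Who learns it.** The data collector. The role is not separate from outcome assessment. Section 10.1.8 trains data collectors for both baseline and follow-up. Section 8.2 has the data collector respond to a high depression score obtained as part of outcome assessment. In the parent trial, Section 8.1 uses the term for the very staff who must be masked: "Centralized data collection maintains data collectors being blind to group assignment".

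3. **Whether the same person makes the later calls.** The continuity rule in Section 5.5 says yes, where possible. The list containing it follows text on the supplement cohort study, so its attribution has to be inferred. Its content fits the pilot:
   - It includes the item "make confirmation phone calls 2 days prior to the baseline and/or the SPIRIT session (intervention group", whereas the cohort study delivers no SPIRIT session.
   - It offers transport support for that session.
   - It pays surrogates for an assessment 1 month after a death, which is the pilot's time point and not the parent trial's 3 months.
   - Cohort-study payments are given separately after the list.

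   The parent trial's own list carries the same continuity rule.

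4. **Whether another rule rescues the blinding.** None was found. No section names a separate masked assessor for the pilot's 2-3 day or 1-month calls, and none gives the envelope to anyone else.

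5. **Who is exposed.** The envelope is opened for every randomised dyad, in both arms, so up to 30 of 30 dyads could be assessed at 2-3 days by someone who knows the arm. For the post-death assessment, the plan expects 50% mortality, so 0.50 × 30 = 15 surrogates, the number given in Section 9.4.2.

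6. **A related inconsistency.** Section 6.3 has the data collector book the follow-up call, while Section 6.2.1 has the interventionist do so after the SPIRIT session. Section 6.2.1 does not cover usual-care dyads.

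**The case against.** The best defence is that no sentence says the envelope-opener makes the outcome call. Section 6.3 has that person schedule the follow-up session, not conduct it. The continuity rule is generic and conditional, while the blinding statement is specific to the pilot. Both can hold if an unmasked collector is treated as unavailable for the outcome call. This is a fair reading, and it rules out the stronger claim a reader might infer, that the pilot's assessors are in fact unblinded. But it depends on staff setting aside a written retention rule, and the plan does not tell them to.

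A second defence concerns harm. Dyads know their arm, the instruments have fixed responses, the outcomes are self-reported, and Section 10.1.8 trains collectors in scripted techniques. Response bias from unblinded dyads exists whoever calls. This also stands, and it rules out a second tempting inference, that the effect sizes would be inflated. The documents support only that they could be biased, by an unknown increment.

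Third, the care-decision outcome is outside this argument, because the research coordinator tracks it through clinic staff. That is correct.

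**Conclusion.** The point holds as a gap between a stated safeguard and the procedure meant to deliver it. Following the plan as written would usually leave the follow-up caller aware of the arm, for up to 30 dyads at 2-3 days and about 15 expected surrogates at 1 month after a death. Because the continuity rule is conditional, the actual number could be smaller.

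The conclusion rests on two inferences: that the Section 5.5 list belongs to the pilot, and that the data collector who does baseline is the one kept for follow-up. The text supports both but states neither outright. The size of any bias cannot be derived from the documents.

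The point concerns the pilot's interviewer-collected outcomes only, not its baseline scores and not the parent trial. It should be corrected, because the written rule works against the only masking claimed and the correction is simple.

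**What to change.** Amend Section 6.3 so that, once the collector reports baseline complete, the interventionist or another existing staff member who assesses no outcome opens the envelope. That person books the SPIRIT session and, in both arms, the follow-up call. The collector then stays masked and the same-collector rule can remain. The research coordinator should not take this task, because that role tracks care decisions, which are a Supplement Aim 1 outcome.

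If the collector must open the envelope, exempt the outcome calls from the same-collector rule and assign them to a different, masked collector. Failing that, withdraw the blinding statement for the pilot.

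In either case, reconcile Sections 6.2.1 and 6.3 on who schedules the follow-up call, and say who does so for usual-care dyads. If calls have already been made, report who made them and whether that person had opened the envelope.

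The cost is a small reassignment of tasks among existing staff. The documents do not give the number of pilot data collectors, so the alternative of a second collector may be harder to staff than the main proposal.

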6.4 STUDY INTERVENTION COMPLIANCE

To maintain internal validity, certain components of the intervention will be standardized: standardized care provider training using the training modules (described above); Session 1 will be delivered via face-to-face; the SPIRIT Interview Guide will be used during each session to promote consistency and quality of intervention delivery. We will develop a template of procedures related to SPIRIT implementation for each clinic to customize and use as a resource.

To assess fidelity, we will use two independent data sources.

- 1) The SPIRIT Interview Guide will direct the care provider to document performance data after each patient-surrogate dyad encounter (the data will be entered into REDCap by each site coordinator). The Guide has a checklist of SPIRIT components, including start and finish times and brief self-evaluation.
- 2) At the 2-week post-intervention follow-up, a research assistant will query patients and surrogates about the SPIRIT sessions using the checklist of SPIRIT components. After the first 50 dyads (\sim first 4 months) have been seen, clinics with $<80\%$ adherence on both data sources will receive feedback and another orientation meeting by the Site PI and the SPIRIT trainer.

We considered replacing clinics with $<80\%$ adherence, but this approach would not be consistent with the pragmatic nature of the study to test SPIRIT in a real-world setting. We also considered recording a sample of SPIRIT sessions, but this approach would likely be considered intrusive by the dialysis care providers and is unrealistic in a pragmatic trial.

For Supplement Aims:

To promote consistency and quality of intervention delivery, the SPIRIT Interview Guide will be used during each session. To monitor fidelity, we will use two data sources. 1) The SPIRIT Interview Guide will direct the interventionist to document performance data after each patient-surrogate dyad encounter; these data will be

entered into the Research Electronic Data Capture (REDCap) by the research coordinator. The Guide has a checklist of SPIRIT components, including start and finish times, and brief self-evaluation. 2) All intervention sessions will be audio-recorded. Every 2 months, 50% of sessions randomly selected will be reviewed by the PI. Using the Treatment Fidelity Assessment Tool, the interventionist's adherence to intervention content, process, and duration will be evaluated on a 3-point scale (1=appropriate, 3=skipped). Problems detected including drift from protocol will be discussed with the interventionist and re-training will be provided if adherence is <80% based on the Fidelity Assessment Tool.

6.5 CONCOMITANT THERAPY

Not applicable (all patients receive usual care related to advance care planning).

6.5.1 RESCUE MEDICINE

Not applicable.

7 STUDY INTERVENTION DISCONTINUATION AND PARTICIPANT DISCONTINUATION/WITHDRAWAL

7.1 DISCONTINUATION OF STUDY INTERVENTION

SPIRIT is a one-time intervention with two sessions. If patient-surrogate dyads is not able to complete Session I or II, the reason or circumstances (e.g., the patient became too ill) will be documented and reported. Session II cannot be offered without Session I completed; that is, it is possible that a patient-surrogate dyad completes Session I but not Session II. Dyads who never complete Session I and dropout will be replaced by enrolling a new dyad.

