Three RCTs testing SPIRIT¹⁸⁻²⁰ were conducted in free-standing outpatient dialysis settings and established the feasibility, patient and surrogate acceptability, preliminary effects (R21NR009662), and efficacy of SPIRIT delivered in those settings by trained research nurses. Dialysis facilities varied in type, including profit and non-profit ownership, urban and rural, and academic affiliation and community. The PI ([name]) has the intimate knowledge of implementing SPIRIT in these complex health care systems. Recruitment rates have consistently been over 80% with a very low dropout rate (<4%). Throughout these trials, we have tested strategies and procedures related to recruitment, retention, data collection, and SPIRIT training, fidelity, and measurement.

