5.4 SCREEN FAILURES

Because patients are approached first at the dialysis center, it is possible that patients provide written consent to participate in the study with the assumption that their surrogates would be willing to participate with them (however, patients cannot complete the baseline without willing surrogates), and then the surrogate actually declines to participate. Because randomization occurs at the clinic level, not the individual level, these cases will be reported under "not eligible" with reason.

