Recruitment will occur over 24 months beginning at the end of Year 1. We are highly experienced in recruiting seriously ill ESRD patients and their surrogates for research. Consent rates in our previous studies have been consistent at approximately 84% despite the studies' focus on end-of-life, the requirement that both patient and surrogate participate, and long-term follow-up. We expect a similar if not higher consent rate because the study involves a shorter follow-up time and minimal data collection directly from patients and surrogates. Based on our previous studies,¹⁸⁻²⁰ we conservatively anticipate that 427 patients (20%) will be *eligible and willing* to participate. To reach 400 dyads, we expect to enroll 21-22 dyads per cluster on average. These clinics each accept 10-70 new patients each year (total 700 additional patients), and thus our recruitment goal is readily achievable.

To Maximize Participant Retention, strategies found effective in retaining dyads over 12 months (dropouts, 3.8%) in our efficacy trial²⁰ will be used: we will

- a) obtain two backup contacts from each member of the dyad in the event that we cannot reach them by telephone and mail
- b) make confirmation phone calls 2 days prior to each follow-up
- c) make monthly check-in calls
- d) send holiday cards
- e) assign the same data collector whenever possible
- f) compensate each member of the dyad with gift cards (\$15 at baseline, \$15 at 2 weeks for the preparedness outcome assessment; \$20 at 3 months for the post-bereavement outcome assessment). Consistent with a pragmatic trial, participants will not be compensated for participating in the intervention. The Emory Study Coordination Center will be responsible for disbursement.

For Supplement Aims:

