7.2 PARTICIPANT DISCONTINUATION/WITHDRAWAL FROM THE STUDY

Participants are free to withdraw from participation in the study at any time upon request.

An investigator may discontinue or withdraw a participant from the study for the following reasons:

- If the participant meets an exclusion criterion that precludes further study participation.

The reason for participant discontinuation or withdrawal from the study will be recorded on the study REDCap. Subjects from the dialysis center randomized to initial SPIRIT who sign the informed consent form but do not receive the study intervention may be replaced. Subjects in the initial SPIRIT who sign the informed consent form and receive the study intervention, and subsequently withdraw, or are withdrawn or discontinued from the study will not be replaced.

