7.3 LOST TO FOLLOW-UP

Patients lost to follow-up will not be applicable in this trial since all patients must come to the dialysis center for their treatment and thus can be contacted at the center.

A surrogate participant will be considered lost to follow-up if he or she fails to complete the scheduled 2-week follow-up (after the receipt of the intervention) and is unable to be contacted by the study site staff until the end of the 9-month follow-up period. Or, a surrogate participant will be considered lost to follow-up if he or she fails

to complete the scheduled 3-month follow-up (after the patient's death) and is unable to be contacted by the study site staff.

The following actions must be taken if a participant is determined to be lost to follow-up:

- The site will attempt to contact the participant and reschedule the missed appointment for 4 weeks and ascertain if the participant wishes to continue in the study.
- Before a participant is deemed lost to follow-up, the investigator or designee will make every effort to regain contact with the participant (where possible, 3 telephone calls and, if necessary, a certified letter to the participant's last known mailing address or local equivalent methods, or speak to the patient at the dialysis center). These contact attempts will be documented in the participant's record in REDCap.
- Should the participant continue to be unreachable, he or she will be considered to have withdrawn from the study with a primary reason of lost to follow-up.

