9.3 POPULATIONS FOR ANALYSES

Patient-surrogate dyads will be the primary unit of analysis; all analyses will be intent to treat with all available data from all participants.

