- 4) Aim 3. Relationships among patients' cognitive status, decision-making capacity and their ability to express end-of-life wishes:** For patients in the SPIRIT intervention arm (n=15), associations between patients' cognitive status (continuous), decision-making capacity (continuous) and their ability to express end-of-life wishes (categorical) will be analyzed using one-way analysis of variance (ANOVA). We will also explore ordinal logistic regression to obtain the proportional odds ratios defined by the odds of "expressing wishes very coherently" or

“expressing wishes somewhat coherently” versus the odds of “unable to express wishes coherently” for a unit increase in cognitive status or decision-making capacity.

Supplement cohort study:

As in the parent R01, we will use the Research Electronic Data Capture (REDCap) to create and update study participants’ data. During data entry, automated checks will be performed that will immediately flag problematic data (e.g., missing, out of range, inconsistent). Preliminary analyses will include summarizing variables with descriptive statistics and graphical displays. We will assess distributional assumptions of the outcomes and apply appropriate transformations to remedy any violations. Any differences in patient characteristics (e.g. age, sex, education level, household income) across groups will be adjusted when modeling the outcomes. As observed in the parent R01 (< 1% missing data), we expect very little missing data. Nonetheless, we plan to use restricted maximum likelihood (REML) method for estimating the repeated measures analysis to minimize the impact of missing data. This will make it possible to retain cases with partial data while making less restrictive assumptions about missing data patterns.

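### No 2-week assessment date is set for a SPIRIT dyad that stays in the study without completing its sessions, while every control dyad has one

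*Combined protocol and SAP*

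**What the plan says.** **Replacement.** Section 7.1: "Dyads who never complete Session I and dropout will be replaced by enrolling a new dyad". Section 7.2 covers subjects from centers "randomized to initial SPIRIT who sign the informed consent form but do not receive the study intervention may be replaced". Those who received the intervention and later withdraw are not replaced. There is no replacement rule for usual care.

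**Timing of T2.** The schedule of activities (1.3) counts the SPIRIT-arm 2-week follow-up from SPIRIT, and 8.1 counts it from Session II. Section 1.3 books that follow-up in the same step as the two sessions. For controls, 1.3 books T2 together with T1.

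**Loss to follow-up.** In 7.3, the surrogate trigger at 2 weeks is a missed assessment after the intervention was received. For patients, loss to follow-up is said not to apply because "all patients must come to the dialysis center for their treatment and thus can be contacted at the center".

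**General statements.** The synopsis (1.1) and the measurement table in section 3 give a 2-week follow-up to patients and surrogates without requiring that sessions took place. Section 9.3: "all analyses will be intent to treat with all available data from all participants".

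**The concern.** The trial asks whether SPIRIT works when clinic staff deliver it as part of ordinary dialysis care. Some dyads in that setting will not start, and 7.1 itself gives a patient becoming too ill as an example of why. Such dyads belong in the estimate.

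A SPIRIT dyad that never has Session I, or has Session I but not Session II, has no anchor for the T2 timing in 8.1. If staff follow the timing as written, that dyad may never be called at 2 weeks. A control dyad with the same illness course would be called, because its date was fixed at baseline. The SPIRIT sample at the primary time point would then be filtered by something that happened after allocation, and the control sample would not. An intent-to-treat analysis of all available data cannot repair this if the outcome was never sought.

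**Working it through.** **Step 1. The passages side by side.**

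| Situation | SPIRIT arm | Control arm |
|---|---|---|
| How T2 is dated | From SPIRIT or Session II (1.3, 8.1) | Booked with T1 (1.3) |
| Sessions do not happen, dyad stays in the study | No date or instruction stated | Does not arise |
| Surrogate misses T2 | 7.3 trigger applies after receipt of the intervention | No separate control rule |
| Replacement | Mandatory if the dyad also drops out (7.1); optional if untreated (7.2) | None |

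Some 7.2 cases arise before baseline, because the patient signs first and "patients cannot complete the baseline without willing surrogates". Section 5.4 already reports surrogate refusals as not eligible, so they are outside this point.

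**Step 2. How many dyads.** The documents give no never-start rate. The nearest figures are under 1% missing data in the parent trial (9.4.2, cohort supplement), under 4% dropout in earlier trials (2.2) and 3.8% dropout over 12 months in the efficacy trial (5.5). I use 1% to 4% as an assumed range and place all of it in SPIRIT. With equal arms (assumed), 400/2 = 200 dyads, so 1% = 2 and 4% = 8.

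**Step 3. A check on the variance formula.** The plan gives no figure for this point, so I tested the design-effect approximation on its power table. With m = 400/19 = 21.05 and DE = 1 + (m − 1) × ICC, power for patient decisional conflict (difference 0.24, variance 0.23) is 0.995 at ICC 0.01 and 0.823 at ICC 0.10, against 0.98 and 0.81 stated. The congruence rows do not reproduce this way (0.82 and 0.72 against 0.92 and 0.84, taking 48% as the control rate). The plan used a simulation whose settings are not given, so I do not call that an error.

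**Step 4. Bias and type I error for congruence.** If a share f of SPIRIT dyads is unmeasured and their rate differs from the starters' rate by a gap g, the bias is f × g. Inputs: rate 48% (9.2), g = 0.20 (assumed; not in the documents), no baseline adjustment, no true effect.

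SE = sqrt(2 × 0.48 × 0.52 × DE / 200); type I error = P(|Z + bias/SE| > 1.96).

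| Clusters | ICC | DE | SE | f = 1% (bias 0.2 points) | f = 4% (bias 0.8 points) |
|---|---|---|---|---|---|
| 19 (9.2) | 0.02 | 1.401 | 0.0591 | 0.0501 | 0.0521 |
| 19 | 0.04 | 1.802 | 0.0671 | 0.0501 | 0.0516 |
| 28 (6.3: 4+3+8+5+8) | 0.02 | 1.266 | 0.0562 | 0.0501 | 0.0523 |
| 28 | 0.04 | 1.531 | 0.0618 | 0.0501 | 0.0519 |

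With g from 10 to 30 points, f = 4%, 19 clusters and ICC 0.02, the bias is 0.4 to 1.2 points and type I error 0.051 to 0.055.

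**Step 5. When it would matter.** At g = 0.20 and ICC 0.02, type I error reaches 0.06 at f = 8.7% (19 clusters) or 8.3% (28 clusters), and 0.10 at 19.3% or 18.3%. For decisional conflict with 19 clusters and non-starters assumed half an SD worse, f = 5% gives 0.056 at ICC 0.01 and 0.052 at ICC 0.10; f = 10% gives 0.074 and 0.060.

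**Step 6. Effect of measuring non-starters.** If 48% is the SPIRIT rate and OR = 2.0, the control odds are (0.48/0.52)/2 = 0.4615, a rate of 31.6% and a difference of 16.4 points. If non-starters gain nothing, the difference becomes 16.4 × (1 − f): about 16.3 at 1% and 15.8 at 4% (16.42 × 0.96).

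**The case against.** The case against is substantial, and much of it stands.

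- **Replacement is not the source of bias.** Clusters are randomised first and dyads are recruited afterwards, so a replacement from the same cluster is in the same randomised arm. That is continued recruitment toward 400, and the bias formula has no replacement term. A reader might infer that one-sided replacement breaks intent to treat. The documents do not support that: nothing removes the replaced dyad, and 9.3 covers all participants in general terms.
- **7.1 and 7.2 differ but do not conflict.** One is mandatory for never-starters who also drop out; the other is optional for any untreated subject. Only SPIRIT has a session to miss, so the one-sided trigger is partly inherent.
- **A 2-week follow-up is listed for everyone** in 1.1 and section 3, and 1.3 books the SPIRIT date along with the sessions. The plan nowhere says T2 is withheld from non-starters. What remains is that no date or instruction applies once the sessions fail.
- **The arithmetic leans toward harm.** The rates are whole-trial figures, one of them over 12 months, and I put all the loss in one arm. Similar loss and similar gaps in both arms would largely cancel. For the cohort supplement the plan says: "As observed in the parent R01 (< 1% missing data), we expect very little missing data".

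On the other side, the low dropout rates come from trials in which research nurses delivered SPIRIT, and the missing-data figure does not say whether replaced dyads are counted. They do not establish a low never-start rate when clinic staff deliver it.

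**Conclusion.** A minor point, and it rests on T2 collection alone. The SPIRIT-arm timing and the surrogate loss-to-follow-up trigger depend on delivery, the control timing does not, and no section says what happens at 2 weeks to a dyad that stays in the study without completing its sessions.

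At an assumed 1% to 4% of SPIRIT dyads and an assumed 20-point gap, the bias in congruence is 0.2 to 0.8 points and type I error is 0.050 to 0.052. The direction is unknown, since non-starters could score worse or better, and if they do not differ there is no bias. A reader might infer a threat to the primary result. The documents do not support that: it would take non-starting well above the rates they report, and they give no never-start rate. Dyads that truly drop out, the group 7.1 names, will mostly stay missing whatever is changed.

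**What to change.** - **7.1 to 7.3 and 8.1:** state that T2 is sought from every dyad that completed baseline and has not withdrawn consent. If Session I or II did not take place, use the date already booked. Apply the contact steps in 7.3 to these dyads too.
- **9.3:** confirm that these dyads, replaced or not, are analysed in their cluster's randomised arm.
- **Reporting:** give non-starters, replacements and missing T2 by arm. Reasons for non-completion (7.1) and counts of incomplete sessions (8.1) are already to be recorded.

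The cost is a few sentences and, at the assumed 1% to 4%, about 2 to 8 extra dyad assessments by the central telephone staff. The expected effect may be slightly smaller, about 15.8 instead of 16.4 points at 4% if non-starters gain nothing. Merging 7.1 and 7.2 would read more clearly but is editorial.
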